12. STATISTICS

12.1. Trial Objectives and Design

The main objective of this study is to assess the efficacy and the safety of I10E in CIDP patients. The design is a phase III, international, multicentre, single arm, open-label prospective study.

12.2. Statistical Analysis Plan

This section is the basis for the Statistical Analysis Plan (SAP) of the study.

The detailed technical aspects of the statistical analyses will be provided in the SAP. The SAP will possibly take protocol amendments into account and adapt to unexpected issues raised by the study running and/or data that affect planned analyses in the protocol.

Any changes from the protocol will be discussed in the clinical study report.

Prior to locking the database, a data review meeting will be planned in order to review individual data and validate the SAP.

12.3. Sample Size Determination

The study is designed to demonstrate superiority of I10E to an historical control in terms of responder rate. The historical responder rate with placebo is estimated from the ICE study [10]. As a conservative estimate the upper boundary of the 95% confidence interval (CI) of the observed rate is used (observed rate $12/58 = 20.7\%$, 95% CI [11.2%, 33.3%]). Based on this historical placebo responder rate of 33.3% and a 60% responder rate with I10E, 38 evaluable patients are needed in order to obtain 90% power using an exact binomial test with a one-sided nominal level of significance $\alpha=2.5\%$. Presuming a 10% non-evaluable patients, 42 patients will be included in the study (around one third of all patients will be either Ig-naïve or relapsing Ig-pretreated).

12.4. Randomization

Not applicable

12.5. Protocol Deviations and Analysis Sets

All deviations from protocol definitions will be listed and defined as major or minor deviations in the SAP.

The definition of analysis sets is as follows:

- Total Treated Set (TTS): all patients who received at least one administration of study drug.
- Full Analysis Set (FAS): all TTS patients having an available assessment of the primary efficacy endpoint.
- Per Protocol Set (PPS): all FAS patients without any major deviations from protocol.

The TTS will be used for the analysis of safety data.

The FAS will be used for the primary analysis of efficacy data and the PPS to test its robustness.

12.6. General rules for handling of missing or inconsistent data

No general rules for the replacement of missing data are planned. Every effort should be made to collect the study parameters over the study period.

12.7. Demographic and baseline characteristics

All baseline characteristics and baseline efficacy variables will be summarised using descriptive statistics on relapsing Ig-pretreated patients, Ig-naïve patients and overall. All summary tables will describe the variables according to their nature:

- Categorical variables (binary, nominal and ordinal) will be summarised by contingency tables (frequencies and percentage),
- Quantitative variables will be summarised by their mean, standard deviation, median, minimum and maximum values.

12.7.1. Previous Treatments

All previous treatments will be classified using the ATC codes and summarised.

12.8. Study drug and concomitant treatments

All variables will be summarised for the subgroups of relapsing Ig-pretreated patients and Ig-naïve patients as well as overall.

12.8.1. Extent of Exposure

The duration of treatment exposure will be assessed as from the first day of study drug administration to the EOS assessment.

The number of infusions, cumulative dose (g and g/kg), volume infused, duration of infusion, infusion rate (initial rate and maximum rate) will be described using descriptive statistics. The treatment exposure will also be listed for each patient.

12.8.2. Treatment Compliance

The following compliance criteria will be described:

- Prescribed course dosage included in the ranges allowed by the protocol
- Course frequency included in the ranges allowed by the protocol
- Courses administered at each visit.
- Ratio administered dose / prescribed dose within 20%.

12.8.3. Concomitant Treatment

All concomitant treatments as defined in Section [7.2](#) Concomitant medication will be classified using the ATC codes and summarised.

12.9. Efficacy Analysis

All efficacy endpoints will be analysed overall and by subgroups of relapsing Ig-pretreated patients and Ig-naive patients.

12.9.1. Primary Efficacy Variable(s)

12.9.1. 1. Description of the primary efficacy variable(s)

The primary efficacy endpoint will be the responder rate at EOS visit.

Responder patients are defined as patients with a decrease of at least 1 point in the adjusted INCAT disability score between baseline and the EOS visit.

If a patient is treated with a not-allowed treatment during the study period, then all efficacy variables measured after the intake of these not-allowed treatments will be censored for the efficacy analyses.

12.9.1. 2. Hypothesis Test and Primary Analysis Model

The responder rate will be tested against the historical responder rate of 33.3% with a one-sided Clopper-Pearson test (exact binomial test) at the nominal level of significance of 2.5%.

The null and alternative hypotheses are as follows:

$$H_0: \pi_{(110E)} \leq 33.3\%$$

$$H_a: \pi_{(110E)} > 33.3\%$$

The proportion of responders and the associated 95% confidence interval will be estimated using a Clopper-Pearson method. The primary analysis will be performed on the FAS.

12.9.1. 3. Handling of Missing Data

The primary analysis of the primary criterion will be done using the baseline and last available assessment of the adjusted INCAT disability score after the first study drug administration. If the score at EOS visit is missing, then the Last Observation Carried Forward (LOCF) approach will be applied and the last available adjusted INCAT disability score will replace the missing value at EOS visit. Other imputation methods might be defined in the SAP for the purpose of sensitivity analyses.

12.9.1. 4. Prognostic factors and covariates

No prognostic factors will be used in the statistical model.

12.9.1. 5. Other analyses for the primary variable

The analysis of the primary criterion will be repeated on the PPS as sensitivity analyse.

Other sensitivity analyses might be defined in the SAP.

12.9.2. Secondary efficacy variables

12.9.2. 1. Description of secondary efficacy variables

- Responder rate at 12 weeks.
- Time to response.
- Percentage of patients at 12 weeks and EOS visit with no change in CIDP treatment.
- Changes from baseline to 12 weeks and EOS visit in the following scores:
 - Adjusted INCAT disability score;
 - Grip strength with the Martin vigorimeter in both hands;
 - Rasch-built Overall Disability Scale (R-ODS);
 - Patient and Investigator Clinical Global Impression (CGI);
 - Medical Research Council (MRC) 12 muscles sum score (0 to 5) and Rasch-modified MRC (0 to 3).

12.9.2. 2. Analysis of secondary efficacy variables

All parameters as well as the change from baseline will be summarised using Hodges-Lehmann point estimates and corresponding confidence intervals. Time to response will be analysed using a Kaplan-Meier method.

If a patient is treated with a not-allowed treatment during the study period (Plasma exchange, blood products or derivatives other than the study drug, immunomodulatory/immunosuppressant agents, corticotherapy, if administered with an increasing dosage or introduced orally or systematically at a dose higher than 10 mg daily prednisolone or equivalent), then all adjusted INCAT disability scores measured after the intake of these not-allowed treatments will be censored for the efficacy analyses.

A LOCF approach will be used to handle the missing data of secondary endpoints. All details to handling of missing data will be provided in the SAP.

The 12-week and the EOS visit values will be compared to the baseline value using appropriate statistical tests. A significance level of 5% (two-sided) will be applied.

The adjusted INCAT disability score will additionally be presented graphically over the patients' follow-up during the study.

12.10. Safety Analysis

All safety analyses will be performed on the subgroups of relapsing Ig-pretreated patients and Ig-naive patients as well as overall.

12.10.1. Adverse events

All AE will be classified using MedDRA including Lowest Level Terms (LLT), Preferred Terms (PT) and System Organ Class (SOC).

TEAEs defined as AEs occurring after the start of the 1st study drug administration will be analysed. Other AEs will only be listed.

The absolute number of TEAEs as well as the number of patients with at least one TEAE will be tabulated by SOC and PT. Patients with SAEs, drug-related AEs will be analysed by SOC and PT.

The duration of the TEAE and the time between the last administration of study drug and the onset of the TEAE will be calculated.

TAAEs will be analysed by patients and infusions.

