- TEAEs by Action taken with IMP (None / Dose reduced / Dose increased / Discontinuation of IMP / Temporary interruption of IMP, (the action could also be a decrease of infusion flow rate))
- TEAEs by outcome (Resolved without sequelae / Resolved with sequelae / Not recovered / Recovering / Fatal / Unknown)
- Other significant AEs

A similar summary table will be produced for TAAEs as well as drug-related TEAEs and Serious TEAEs.

All TEAEs, SAEs, TAAEs and drug-related AEs will be summarized by SOC and PT, showing number of TEAEs, and number and percentage of patients with at least one TEAE, sorted by decreasing incidence of SOC and PT within SOC in the column “overall”.

Summary of TEAEs will also be presented by relevant subgroups (e.g., by age group [<65 years and ≥ 65 years], sex, race [white, non-white and unknown], and BMI [<30 kg/m² and ≥ 30 kg/m²]).

The rate of TEAEs by patient, course, infusion and drug-related AEs by course will be presented and sorted by decreasing incidence of PT in the column “overall”. Rate is defined as the number of events for unique PTs divided by the total number of patients, courses and infusions respectively.

Duration of most-common (those which occurred in at least 10% of the patients in the overall safety population) drug-related AEs will be calculated as is outlined in Section [5.7.2](#) and will be presented with descriptive statistics on recovered AEs (i.e., AEs with an outcome of “Recovered without sequelae” or “Recovered with sequelae”). Statistical unit of analysis will be the individual who recovered from drug-related AE. No imputation will be performed for the purposes of computing duration.

The time between the stop time of the last administration of IMP (before the onset of event) to the onset of the drug-related AEs will be calculated (in days) as is outlined in Section [5.7.2](#) and will be presented with descriptive statistics using the individual drug-related AE as statistical unit.

All Serious TEAEs, drug-related AEs, AEs leading to dose changes (action taken is not missing, “None” or “Not-applicable”) or discontinuation of IMP, and other significant TEAEs will be listed. These listings will include the event duration as well as the time elapsed (in days as is outlined in Section [5.7.2](#)) between the stop time of the last administration to the onset of the event.

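### The SAP summarises adverse-event onset time only for drug-related events, and duration only for common, recovered, drug-related ones. The protocol sets no such limits and the SAP does not declare the change.

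*Protocol*

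**What the plan says.** Protocol 12.10.1 defines TEAEs as events after the start of the first administration and then states: "The duration of the TEAE and the time between the last administration of study drug and the onset of the TEAE will be calculated". Nothing in that section limits either calculation to related, frequent or resolved events.

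SAP 4.7.2 narrows both:

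- **Onset time.** The interval from the end of the last administration "to the onset of the drug-related AEs will be calculated (in days", and it "will be presented with descriptive statistics using the individual drug-related AE as statistical unit".
- **Duration.** "Duration of most-common (those which occurred in at least 10% of the patients in the overall safety population) drug-related AEs will be calculated", and the result "will be presented with descriptive statistics on recovered AEs". Three filters therefore apply: related, in at least 10% of patients, and recovered.

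The same section plans two other outputs that bear on timing. The first is tabulation: "All TEAEs, SAEs, TAAEs and drug-related AEs will be summarized by SOC and PT". TAAEs are identified from the eCRF schedule item (during infusion, or within 72 hours of its end), not from relatedness. The second is a set of listings. They cover "All Serious TEAEs, drug-related AEs, AEs leading to dose changes (action taken is not missing" and so on through discontinuations, "and other significant TEAEs will be listed. These listings will include the event duration as well as the time elapsed" since the last administration.

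SAP 5.7.2 gives formulas for duration and time to onset for AEs in general. SAP 4.10.2 lists two safety changes from the protocol: the timing of vital signs and the added haemolysis analysis.

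**The concern.** There are two issues.

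The first is delivery. A programmer who follows SAP 4.7.2 will not produce what protocol 12.10.1 describes. SAP 4.10.2 records a change as small as whether vital signs were taken before each infusion or each course, so a reader would expect this narrowing to appear there too.

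The second is selection. The trial is single-arm and open-label, with no concurrent background event rate, so the timing of events within the three-week cycle is useful safety information. The planned onset summary contains only events that an investigator, who knows the infusion dates, has called related. If nearness to an infusion makes that call more likely, the summary leans towards early onsets, and later events tend to be left out. The duration summary has a further lean: events that have not resolved are excluded, which favours shorter durations.

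**Working it through.** The plan states no figure on this point, so there is none to reproduce. The check is a comparison of text, followed by arithmetic for scale.

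**1. Scope of each output**

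| Output | Events covered | Source |
|---|---|---|
| Duration and onset time, calculated | All TEAEs | Protocol 12.10.1 |
| Onset-time statistics | Drug-related AEs | SAP 4.7.2 |
| Duration statistics | Drug-related, in at least 10% of patients, recovered | SAP 4.7.2 |
| Listings with both variables | Serious TEAEs, drug-related AEs, AEs with a dose change or discontinuation, other significant TEAEs | SAP 4.7.2 |
| TAAE tables (yes/no at 72 hours) | All causalities | SAP 4.7.2 |
| Declared safety changes | Vital signs and haemolysis only | SAP 4.10.2 |

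What remains is the TEAE that is non-serious, judged unrelated, led to no action with the study drug and lies outside the selected SMQs. It appears in SOC/PT counts and, if early, in TAAE counts. No specified output gives its duration or onset time.

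**2. The 10% threshold**

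Planned number treated: 42 (protocol 5.1). 0.10 × 42 = 4.2, so an event must occur in at least 5 patients. The chance of reaching that count is the binomial tail P(X ≥ 5) with n = 42, for an assumed true per-patient incidence:

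| Assumed incidence | P(at least 5 of 42) |
|---|---|
| 3% | 0.008 |
| 5% | 0.057 |
| 8% | 0.243 |
| 10% | 0.412 |

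Most uncommon drug-related events would therefore have no duration summary, although each would be listed with its duration.

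**3. How far selection could move the onset summary**

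Assume no drug effect, onsets uniform over a 21-day cycle, and a one-day course. Let *a* be the probability that an event in the first 3 days is called related, and *b* the probability for an event in the other 18 days. The share of related-only onsets within 72 hours is

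3*a* / (3*a* + 18*b*).

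| *a* | *b* | Calculation | Share within 72 h |
|---|---|---|---|
| equal | equal | 3/21 | 14% |
| 50% | 30% | 1.5/6.9 | 22% |
| 50% | 20% | 1.5/5.1 | 29% |
| 80% | 10% | 2.4/4.2 | 57% |
| 90% | 5% | 2.7/3.6 | 75% |

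The values of *a* and *b* are assumptions; the documents give none. The 14% benchmark is itself a lower bound. Courses may last 2 to 5 days at first and 1 to 2 days later (protocol 3.1.4), and each infusion restarts the clock.

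**The case against.** The strongest reply is that the SAP already provides a view of timing that does not depend on causality. TAAEs are defined by time from infusion and tabulated by SOC and PT. TEAE and TAAE counts also stand together in the overall summary, so the all-cause share near infusion can be read directly. This stands. A reader might infer that the plan has no look at timing free of the investigator's opinion; the documents do not support that. A yes/no split at 72 hours is not an onset distribution, however, and shows nothing about clustering later in the cycle.

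A reader might also infer that timing is reported only for related events. That is true of the summary statistics but not of the SAP as a whole. Serious, action-leading and SMQ events are listed with both variables whatever their causality, and SAP 5.1 promises listings of all data. Haemolysis is also assessed per course from laboratory criteria, and thromboembolic signs by visit, so delayed effects of those kinds are not hidden by a causality call.

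Thirdly, the protocol says these quantities will be calculated, not tabulated; its section 12.2 leaves technical detail to the SAP; and SAP 5.7.2 has general formulas. This reduces the gap to one of reporting scope and disclosure, but does not close it, because SAP 4.7.2 specifies output only for restricted subsets.

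Finally, the 10% threshold is a common presentation choice, and quartiles on four or fewer values say little. That is fair, and it is a reason to keep the row as an extra.

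**Conclusion.** The concern holds as an undeclared narrowing of descriptive safety reporting. SAP 4.7.2 conditions the onset summary on relatedness, and the duration summary on relatedness, frequency and recovery. Protocol 12.10.1 imposes none of these conditions, and SAP 4.10.2 does not record the change. That conclusion rests on the text alone.

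The distortion is conditional. It is tempting to say that the related-only table will show early clustering even if the product causes nothing, because relatedness is judged from timing. The documents do not support that. The investigator supplies the relationship to study drug (protocol 9.5.3), but the public text gives no criteria for it and does not mention timing among them. The table can be distorted if the judgement leans on timing; by how much is unknown. The range from 14% to 57% or more depends entirely on the assumed rates, and with equal rates there is no distortion.

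The primary endpoint, its test and the efficacy conclusions are not affected.

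**What to change.** In SAP 4.7.2, summarise time from last administration to onset, and duration, for all TEAEs as the protocol states. Show drug-related TEAEs as a subset row. The duration summary for events in at least 10% of patients may stay as an extra row. Add both derived variables to the full TEAE listing. If the sponsor prefers to keep the restriction, declare and justify it in SAP 4.10.2.

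Two inconsistencies should be settled in the same edit, since the wider summaries would inherit them:

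- SAP 4.7.2 measures onset from the stop time of the last administration, while SAP 5.7.2 uses calendar dates plus one day.
- SAP 4.7.2 rules out imputation for duration, while SAP 3.2 imputes partial dates for it.

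The cost is SAP wording, a longer table and two more listing columns. The event and infusion dates are already collected, and general formulas already exist in SAP 5.7.2.

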12.10.2. Vital signs

Vital signs, including body temperature (in °C), heart rate (in beats/minute) and systolic and diastolic blood pressures (in mmHg), will be measured before each infusion, during infusion (30-45 min and 60-75 min after the beginning of infusion) and 30-45 minutes after the end of infusion for all visits. Descriptive statistics will be performed.

All abnormalities in vital signs, clinically significant or not, will be listed.

12.10.3. Laboratory data

Laboratory data will be assessed at screening, before each study drug course, after the 1st study drug course, and at the EOS visit. Shift tables will be produced by study drug courses and baseline. Descriptive statistics will be performed. All abnormalities, clinically significant or not will be listed.

12.11. Exploratory Analysis

The following exploratory endpoints will be analysed:

- Anti-CNTN1 and anti-NF155 antibodies titers at screening and EOS visit.
- FcγRIIB B cells marker levels at visits V2, V3 and V4.
- BAFF and complement components (C3 and C4 antigens, CH50) at visits V2, V3, V4 and EOS visit.
- Serum total IgG trough levels before each study drug administration.
- Change from baseline to EOS visit in nerve conduction velocities, distal latencies, amplitude of the negative phase of compound muscle action potentials and F wave for the following peripheral nerves: median nerve, ulnar nerve and deep fibular nerve (F wave assessed on ulnar nerve only).
- Change from baseline to EOS visit in nerve maximal/minimal cross section area (CSA), intra-nerve and inter-nerve variability and ultrasound (USG) immune-related classification (see Section [1.4.4](#) Peripheral nerve ultrasonography) in the following peripheral nerves: median nerve, ulnar nerve, fibular nerve and sural nerve.

All exploratory variables will be described in summary tables. The relationship between these variables and clinical response will be explored and detailed in the SAP.

13. STUDY REPORT

A clinical study report will be prepared in accordance with the ICH-E3 guidelines by the Sponsor.

Within 1 year after the end of the study, the Sponsor will provide the Health Authorities with the full study report or summary. Only the Sponsor is entitled to make the study report available to the Authorities.

Neither the complete report nor any part of the study report should be used without the approval of the Sponsor.

14. CONFIDENTIALITY AND PUBLICATION

14.1. Patient confidentiality

Patient data will be kept strictly confidential and patient anonymity will be protected by using number codes.

The Sponsor or its representative(s) and the Health Authorities are obligated to respect medical secrecy and to refrain from divulging any personal patient information they might fortuitously be aware of.

14.2. Use of information

The Investigator shall not divulge unpublished data or information related to the study provided by the Sponsor, including but not limited to the study protocol, eCRFs, assay methods and scientific data, to any third party without written approval from the Sponsor.

In addition, any new information that may become available during the course of the study shall be considered as confidential and shall not be used for any purpose other than the performance of the clinical study.

The study data are the property of the Sponsor. The Investigator and any of the research staff shall obtain written approval from the Sponsor prior to the publication/communication of the results of any work carried out during or in relation to the study.

Publication and/or communication of the results of the clinical study will be of a cooperative nature involving authors representing the Sponsor, the Investigators and the scientific committee.

The Sponsor reserves the right to request modification of the content and/or timing of any publication or presentation if a patent application, an existing patent or other proprietary rights may be jeopardized.

Authorship of any publication related to the study and the order of presentation of the authors' names shall be approved by the Sponsor. The Sponsor shall not use an Investigator's name in any publication without his/her written permission and vice versa.

